 To assess the pharmacokinetics (PK) of E-602 as monotherapy. To assess the PK of E-602 in combination with cemiplimab. To evaluate the immunogenicity of E-602 To evaluate preliminary antitumor activity of E-602 as monotherapy in subjects with advanced cancers. 	 Noncompartmental PK parameters of E-602 as monotherapy and in combination with cemiplimab, including the maximum plasma concentration (C_{max}) and area under the plasma concentration-time curve (AUC).

Protocol Number: PAL-E602-001
Version 8.0, 24 August 2023

- To evaluate preliminary antitumor activity of E-602 in combination with cemiplimab in subjects with advanced cancers.
- Number and percentage of subjects who develop detectable antidrug antibodies (ADA).
- Objective response rate (ORR) of confirmed complete response (CR) and partial response (PR) using Response Evaluation Criteria in Solid Tumors (RECIST) v1.1 and Immunotherapy Response Evaluation Criteria in Solid Tumors (iRECIST).
- Duration of response (DOR).
- Progression-free survival (PFS), defined as the time from the first dose to first evidence of radiographically detectable disease or death from any cause, whichever occurred first.
- Overall survival (OS).

Dose Expansion Phase (Phase 2)

Primary

- To evaluate the preliminary antitumor activity of E-602 as monotherapy in subjects with advanced cancers.
- To evaluate the preliminary antitumor activity of E-602 at the combination RP2D in combination with cemiplimab in subjects with advanced cancers.
- ORR of confirmed CR or PR.
- DOR of confirmed CR or PR.
- PFS.
- OS.

Secondary

[figure not shown]
- To evaluate the safety and tolerability of E-602 as monotherapy in subjects with advanced cancers.
- To evaluate the safety and tolerability of E-602 in combination with cemiplimab in subjects with advanced cancers.
- To assess the PK of E-602 as monotherapy.
- To assess the PK of E-602 in combination with cemiplimab.
- To evaluate the immunogenicity of E-602

[figure not shown]
- Incidence of AEs and SAEs graded according to NCI CTCAE v5.0.
- Noncompartmental PK parameters of E-602 as monotherapy and in combination with cemiplimab, including C_{max} and AUC.
- Number and percentage of subjects who develop detectable ADA.

Phase 1 and Phase 2

Exploratory

- To evaluate exploratory pharmacodynamic biomarkers of E-602 activity as monotherapy.
- To evaluate exploratory pharmacodynamic biomarkers of E-602 activity in combination with cemiplimab.

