9.1. Analysis Sets

DLT Evaluable Set:

Will include all subjects treated in the dose escalation part who have had a DLT within Cycle 1 on study or without a DLT but completed safety assessments through Cycle 1 (3 doses of E-602 administered for monotherapy cohorts and 3 doses of E-602 and 1 dose of cemiplimab administered for combination therapy cohorts). The DLT Evaluable Set will be defined for each dose cohort. Subjects who discontinue prior to completing Cycle 1 (3 doses of E-602 administered for monotherapy cohorts and 3 doses of E-602 and 1 dose of cemiplimab administered for combination therapy cohorts) for reasons other than toxicity may be replaced.

Safety Analysis Set:

Will include all subjects who have received any dose of study treatment. The Safety Analysis Set will be used for safety analyses. Safety Analysis Set may be further defined by the phase of the study, dose, and tumor type.

Efficacy Evaluable Set:

Will include all subjects who receive any dose of study treatment, meet eligibility criteria, have measurable tumor lesions at baseline, and have at least one post-baseline disease assessment per RECIST v1.1. Efficacy Evaluable Set is defined for each cohort in the Phase 2 separately.

Pharmacokinetics (PK) Analysis Set:

Will include all subjects in the Safety Analysis Set for whom adequate data on E-602 plasma concentration are available.

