9.2.5. Efficacy analysis

The primary analysis for efficacy will be based on the cohort-specific efficacy evaluable analysis set. Sensitivity analysis may include pooling additional subjects treated in Phase 1 at the same dose level in the same tumor type.

For objective response rate (ORR), the Clopper-Pearson 80% and 95% confidence intervals (CIs) will be provided. Confidence intervals adjusting for the 2-stage nature of the design may also be provided.

Duration of response (DoR) will be calculated among responders (CR and PR). The Kaplan-Meier method will be used to estimate median DoR and the confidence intervals. Subjects who continue to respond at the time of the analysis will be censored at the last assessment of response.

Progression-free survival (PFS) is measured from the date of first study treatment dose until the first date when progressive disease (PD) is objectively documented or death from any cause. Subjects without PD or death will be censored at the last available tumor assessment. PFS will be summarized using the Kaplan-Meier method.

Overall survival (OS) is measured from the date of first study treatment dose until death. Subjects who are alive will be censored at the last known alive date. OS will be summarized using the Kaplan-Meier method.

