 To evaluate the preliminary antitumor activity of E-602 as monotherapy in subjects with advanced cancers. To evaluate the preliminary antitumor activity of E-602 at the combination RP2D in combination with cemiplimab in subjects with advanced cancers. 	 ORR of confirmed CR or PR. DoR of confirmed CR or PR. PFS. OS.
Secondary	
 To evaluate the safety and tolerability of E-602 as monotherapy in subjects with advanced cancers. To evaluate the safety and tolerability of E-602 in combination with cemiplimab in subjects with advanced cancers. To assess the PK of E-602 as monotherapy. To assess the PK of E-602 in combination with cemiplimab. To evaluate the immunogenicity of E-602 	 Incidence of AEs and SAEs graded according to NCI CTCAE v5.0. Noncompartmental PK parameters of E-602 as monotherapy and in combination with cemiplimab. including C_{max} and AUC. Number and percentage of subjects who develop detectable ADA.

Objectives	Endpoints	
Phase 1 and Phase 2		
Exploratory		
• To evaluate exploratory pharmacodynamic biomarkers of E-602 activity as monotherapy.	 Immune cell desialylation and activation using fluorescence-activated cell sorting (FACS) 	
To evaluate exploratory pharmacodynamic biomarkers of E-602 activity in combination with	• Immune cell gene expression profiling (RNAseq; Phase 1 E-602 monotherapy only)	
cemiplimab.	Changes in cytokine levels	
	Changes in circulating tumor DNA	
	Changes in tumor desialylation by immunohistochemistry (IHC)	
	Tumor IHC analysis for immune modulation of different immune cell subtypes	
	• Tumor gene expression and mutation profiling	
	Glycoproteomic profiling	
	• Genetic variation or single nucleotide polymorphisms (SNPs) in select genes (e.g. glycogenes) (Phase 1 combination and Phase 2 only)	

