4.2 Secondary Efficacy Endpoints

Duration of Response (DoR)

Duration of response is defined as the time from the start date of first observed CR or PR (subsequently confirmed) to the date of first documented radiographical progression of disease using RECIST v1.1 or death from any cause, whichever comes first. DoR will be calculated for subjects who are responders, i.e., those who achieve a confirmed CR or PR.

DoR in days will be calculated as:

DoR (days) = [Date of PD, or Death, (whichever is earlier)] – (First Date of PR/CR) + 1 DoR in months will be calculated as:

DoR (months) =
$$[12 \times DoR (days)]/365.25$$

Responders who have not experienced disease progression or death at the time of the analysis will be censored at the date of the last tumor assessment. If no tumor assessments are available after the date of the first occurrence of response, the subject will be censored on the date of the first occurrence of the response.

Progression-Free Survival (PFS)

Progression-free survival is defined as the time from the date of first dose (study day 1) of study treatment to the first documented radiographical progression of disease using RECIST v1.1, or death from any cause, whichever comes first.

PFS in days will be calculated as:

PFS (days) = [Date of PD or Death (whichever is earlier)] – (First Dose Date) + 1

PFS in months will be calculated as:

PFS (months) =
$$[12 \times PFS (days)]/365.25$$

The following table summarizes the PFS censoring rules:

Table 3: Progression-Free Survival Censoring Rules

	Primary Analysis (Censoring Rules)	Sensitivity Analysis (Censoring Rules)
No PD, No death	Censored at last tumor assessment. If no evaluable tumor assessment, censored on the first dose date.	Censored at last tumor assessment. If no evaluable tumor assessment, censored on the first dose date.
PD or death after 1 missed tumor assessment	PFS event at the date of PD or death	PFS event at the date of PD or death
PD or death after 2 or more missed tumor assessments	Censored at last tumor assessment prior to PD or death	PFS event at the date of PD or death
PD or death after NACT	Censored at the last tumor assessment prior to NACT	PFS event at the date of PD or death
No PD, no death, NACT initiated	Censored at the last tumor assessment prior to NACT	Censored at last tumor assessment regardless of NACT

Overall Survival (OS)

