6.1 General Statistical Considerations

In general, all analyses will be summarized by dose level and study treatment (e.g. monotherapy, combination with cemiplimab). Safety analysis will be based on the safety analysis population. The primary efficacy analysis will be based on the efficacy evaluable population by study treatment and/or tumor indication.

For each tumor indication, subjects administered the same study treatment may be combined for analysis purposes, regardless of study phase. Statistical inference, when performed, will be assessed at the 2-sided nominal 5% significance level without multiplicity adjustment. Point estimates will be accompanied by 95% confidence intervals (CIs). For the ORR endpoint assessed per the Simon's 2-stage design, the 2-sided 80% CI may be used.

For continuous variables, the number of observations (n), mean, standard deviation, median, minimum, and maximum will be provided as summary statistics. The mean and median will be reported to one additional decimal place compared to the original data. The standard deviation will be reported to two additional decimal places compared to the original data and the minimum and maximum will be reported to the same number of decimal places as the original data.

For categorical variables, the frequency and percentage in each category will be displayed. Percentages (e.g., for AEs and concomitant medications) will be calculated out of the population total for each cohort. Footnotes will clarify the denominator used in each output if other than the analysis set stated in the title. Percentages will be reported to one decimal place throughout unless the percentage is 100 (in which case no decimal places will be presented) or if the frequency count is zero (in which case no percentage will be presented).

For time to event data, unless otherwise noted, the median value, 25th percentile and 75th percentile will be calculated using the Kaplan-Meier method. The Brookmeyer and Crowley method will be used to calculate the CI of the median value (Brookmeyer and Crowley 1982). Also, the Greenwood formula will be used to calculate the CI of the rate of interest pertaining to the time to event data, at a given time point estimated using the Kaplan-Meier method (Kalbfleisch and Prentice 2002). The time to event analysis will be calculated only if an adequate number of responses are observed to warrant.

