6.3 Efficacy Analyses

The primary efficacy analyses will be based on the efficacy evaluable population. For each tumor indication, subjects administered the same study treatment may be combined for analysis purposes, regardless of study phase. All data from scheduled or unscheduled tumor assessments will be included in the efficacy analyses except for tumor assessments after the initiation of new anti-cancer therapy for the ORR and DoR endpoints as described in Section 4.

Sensitivity efficacy analysis may be performed based on the ITT Population if it is sufficiently different from the efficacy evaluable population and the additional analysis may be informative. Subjects with no measurable baseline disease or no evaluable post-baseline disease assessments (i.e., NE) will be considered non-responders and included in the denominator in the calculation of the ORR for the ITT population.

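### The primary efficacy set leaves out treated Phase 2 subjects with no post-baseline scan, so the reported ORR is biased upward, and the all-treated analysis is only optional

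*Protocol*

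**What the plan says.** Protocol 9.2.5 opens with "The primary analysis for efficacy will be based on the cohort-specific efficacy evaluable analysis set" and then describes ORR, DoR, PFS and OS without naming any other set. Under Protocol 9.1, members of that set must "have measurable tumor lesions at baseline, and have at least one post-baseline disease assessment per RECIST v1.1"; SAP 3.3 has the same condition. SAP 6.1 follows: "The primary efficacy analysis will be based on the efficacy evaluable population by study treatment and/or tumor indication".

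Protocol 8.1 schedules the first scan at week 9 (±1 week), with a scan also planned at end of treatment. Protocol 7.1.2 rules out replacement of Phase 2 subjects. The Simon rule in Protocol 9.4 is written on treated subjects: 16 in Stage 1 and 31 in total.

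The all-treated analysis is in SAP 6.3: "Sensitivity efficacy analysis may be performed based on the ITT Population if it is sufficiently different from the efficacy evaluable population". Only there are subjects with "no evaluable post-baseline disease assessments (i.e., NE) will be considered non-responders". The one sensitivity analysis named in Protocol 9.2.5 is pooling with Phase 1 subjects.

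On endpoint status, the protocol synopsis lists ORR, "DOR of confirmed CR or PR", PFS and OS as Phase 2 primary endpoints. SAP Table 2 does the same ("DoR of confirmed CR or PR" appears beside ORR, PFS and OS). The SAP then defines DoR, PFS and OS under "4.2 Secondary Efficacy Endpoints", analyses them as secondary in 6.3.2 without naming a set, and declares in Section 8 that nothing has changed from the protocol.

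**The concern.** Whether a subject belongs to the primary set depends on what happens after dosing. Someone with no post-baseline scan cannot be a responder, so the scan requirement removes only non-responders. The numerator stays put, the denominator shrinks, and ORR moves in one direction. The reported ORR would also use a different denominator from the decision rule it accompanies.

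For PFS and OS, a subject who dies unscanned has had an event. If the evaluable set applies, as the protocol's wording implies, those early events disappear and every subject analysed has survived at least to a scan.

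These cohorts have no control group. They are judged on absolute figures, with 10% and 25% as the response benchmarks, so a denominator bias passes straight into the result.

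**Working it through.** **Design, reproduced first.** Inputs from Protocol 9.4: continue if at least 2 of 16 respond; promising if at least 6 of 31 respond; null 10%, alternative 25%.

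P(promising) = Σ over x ≥ 2 of b(x; 16, p) × P(Bin(15, p) ≥ 6 − x).

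This gives 0.0788 at p = 10% and 0.8053 at p = 25%, within the stated 0.10 and 80%. An exhaustive search confirms this as the minimax design. The sample size is not at fault.

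**ORR for a given result.** With u unscanned, the evaluable-set ORR is r/(31 − u), which is the all-treated ORR times 31/(31 − u). The values of u are assumptions. Intervals are 80% Clopper-Pearson.

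| Responders | Unscanned | Reported ORR | 80% CI |
|---|---|---|---|
| 6 | 0 | 6/31 = 19.4% | 10.5–31.5% |
| 6 | 2 | 6/29 = 20.7% | 11.2–33.5% |
| 6 | 4 | 6/27 = 22.2% | not computed |
| 6 | 6 | 6/25 = 24.0% | 13.1–38.3% |
| 5 | 0 | 5/31 = 16.1% | 8.1–27.9% |
| 5 | 6 | 5/25 = 20.0% | 10.06–34.0% |

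The last row is a cohort that fails the Simon rule while its reported 80% lower limit sits above the 10% null.

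**ORR on average.** With unscanned probability u, the expected evaluable-set rate is p/(1 − u). At u = 10%: 0.10/0.90 = 11.1% and 0.25/0.90 = 27.8%. At u = 20%: 0.10/0.80 = 12.5% and 0.25/0.80 = 31.3%.

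**How often report and rule conflict.** Each subject is a responder, unscanned, or neither. The exact probability that a cohort reaches Stage 2, ends with at most 5 responders, and still has an evaluable-set 80% lower limit above 10% was computed for true ORR of 10% to 25%. It is below 0.1% at 5% unscanned, 0.6–1.4% at 10%, 2.4–5.0% at 15%, and 5.0–9.7% at 20%.

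**PFS, on the protocol's reading.** With m early unscanned deaths and no other censoring before 6 months, the reported rate is S(6)/(1 − m/31). Assumed true rates of 20%, 30% and 40% become 21.4%, 32.1% and 42.8% for m = 2 (factor 31/29), and 23.0%, 34.4% and 45.9% for m = 4 (factor 31/27).

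**OS, on the protocol's reading.** Let f be the share of deaths before day 63 (2.07 months) that are unscanned. The reported 6-month rate is S(6)/(1 − f × (1 − S(2.07))). The survival curves are illustrative.

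| Median, shape | Deaths before day 63 | True S(6) | f = 25% | f = 50% |
|---|---|---|---|---|
| 6 months, exponential | 21.3% | 50.0% | 52.8% | 55.9% |
| 6 months, Weibull 1.5 | 13.1% | 50.0% | 51.7% | 53.5% |
| 12 months, exponential | 11.3% | 70.7% | 72.8% | 74.9% |
| 12 months, Weibull 1.5 | 4.8% | 78.3% | 79.2% | 80.2% |

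With a 6-month median, f = 100% gives 57.5% (Weibull) to 63.5% (exponential). This is an upper bound only, because of the end-of-treatment scan and the inclusion criterion of more than 12 weeks' life expectancy.

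**The case against.** The strongest reply is that no formal decision changes. The Simon rule is the only Phase 2 criterion and counts treated subjects; everything else is descriptive reporting of preliminary activity. SAP 6.3 already specifies the non-responder rule for an all-treated analysis, and SAP 6.2.1 tabulates set sizes, so a reader can recompute ORR. Making that analysis mandatory would close most of the ORR gap without changing the primary set. The larger distortions need about 6 of 31 unscanned, which is high given the end-of-treatment scan, ECOG 0–1 and the life-expectancy criterion. At 2 of 31 the shift is 1.3 points against an 80% interval about 21 points wide.

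Much of this stands. The decision rule is unaffected. Early progressors who are scanned stay in as PD. The size is unknown and may be small. What it does not remove is the direction of the bias in the headline figure, or the fact that the correction is left to discretion on an undefined trigger. Kaplan-Meier curves cannot be rebuilt from set sizes.

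On PFS and OS the objection is stronger. SAP 4.1 and 6.3.1 treat only ORR as primary, so the evaluable-set sentence in SAP 6.3 can be read as covering ORR alone. The Table 3 rule that censors subjects without an evaluable assessment at first dose does not settle the intended set: it has limited use within the evaluable set, for someone whose only scan is not evaluable. Since the SAP already counts death from any cause as a PFS event, an explicit row for early unscanned death would clarify rather than correct.

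**Conclusion.** The concern holds and should be fixed. For ORR it follows directly from both documents: the primary estimate omits only non-responders, is biased upward whenever anyone goes unscanned, and departs from the denominator of the Simon rule. For PFS and OS the bias follows from the protocol's wording; the SAP leaves the set and the endpoint status unclear, so that part is an ambiguity that would cause bias if resolved the protocol's way.

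The inflation factor for ORR is 31/(31 − u): 1.07 for 2 unscanned, 1.15 for 4 and 1.24 for 6. Every unscanned rate and survival curve used here is an assumption. If everyone is scanned, the scan requirement changes no result. Go/no-go error rates are unaffected provided the Simon rule is applied to treated subjects as written.

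**What to change.** - **Primary set.** In Protocol 9.2.5 and SAP 6.1, 6.3, 6.3.1 and 6.3.2, make all treated subjects the primary set for ORR, PFS and OS in each Phase 2 cohort. For ORR, apply the non-responder rule that SAP 6.3 already states. Keep the evaluable set as a sensitivity analysis.
- **PFS and OS.** In SAP Table 3, add a row making death before the first scheduled scan, with no scan done, a PFS event at the date of death. Keep the existing rows for two or more missed assessments and for new anti-cancer therapy, and keep censoring at first dose for unscanned subjects with neither PD nor death. OS counts every death.
- **Endpoint status.** State once whether PFS and OS are primary or secondary in Phase 2.
- **Simon rule.** Leave it on treated subjects. If 16 and 31 were counted as evaluable subjects while the all-treated ORR was 10%, the type I error would be 0.0956, 0.1164 and 0.1745 at 5%, 10% and 20% unscanned.
- **Minor alignment.** SAP 3.1 defines the treated population by E-602 dosing, Protocol 9.1 by any study treatment; use the protocol's definition. Protocol 9.1 also requires evaluable subjects to meet eligibility criteria and SAP 3.3 does not, although SAP 8 declares no changes; reconcile the two.

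The cost is wording, with no new data or subjects. Editing the protocol is an amendment that needs IRB approval. SAP 1 allows documented modifications, so the SAP could be changed first, with Section 8 updated to say so. Reported ORR, PFS and OS will be less favourable whenever subjects go unscanned.

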9.2.6. Pharmacokinetics and Immunogenicity

Pharmacokinetics

Individual and mean plasma E-602 concentration versus time data will be tabulated, summarized, and plotted by dose level. Noncompartmental PK parameters of E-602 including but not limited to AUC, C_{max}, and C_{trough}, will be tabulated and summarized (e.g., mean, standard deviation, and coefficient of variation). Inter-subject variability and drug accumulation may be evaluated.

Immunogenicity

The number and percentage of subjects who develop detectable ADA will be summarized by dose level. The impact of ADA on PK may be analyzed as appropriate.

9.2.7. Exploratory Analysis: Pharmacodynamics

Serum immune cell desialylation and ctDNA levels will be monitored for potential changes due to the various therapies tested in this study.

9.2.8. Covariates and Subgroup analysis

Additional safety and efficacy subgroup analyses may be performed based on, but not limited to, the following covariates:

- Age or age categories
- Gender (sex at birth)
- Prior anti-cancer treatment
- Baseline PD-L1 expression levels

9.3. Interim Analysis

During the phase 2 portion of the study, the safety data review committee will review both safety and efficacy data. Efficacy data at the end of Stage 1 of the Phase 2 portion will be used to determine Stage 2 expansion. Any additional interim analyses not built in as a part of the study design will be documented.

9.4. Sample Size Determination

Phase 1 Dose Escalation:

Dose escalation for all cohorts will utilize a modified 3+3 design.

A total of 5 dose escalation cohorts are planned for E-602 monotherapy for a total of up to 30 subjects.

A total of up to 2 dose cohorts are planned for the E-602 and cemiplimab combination therapy for a total of up to 12 subjects.

Phase 1 Backfill:

Any Phase 1 cohort may be backfilled up to a total of 15 subjects in a dose cohort (dose escalation and backfill) to obtain additional safety, PK and pharmacodynamic data at a particular dose level.

Phase 2:

For each cohort in Phase 2, Simon's minimax 2-stage design will be used. Sixteen subjects will be treated in the first stage. If ≥ 2 of 16 subjects respond, Stage 2 will be opened to treat an additional 15 subjects for a total of 31 subjects in the cohort. At the end of Stage 2, if ≥ 6 of 31 subjects respond, the treatment will be considered promising for further evaluation. Within each cohort, the design has 80% power and a type I error rate of 0.1 to test the null hypothesis that the response rate is $\leq 10\%$ against the alternative hypothesis of $\geq 25\%$.

10. Supporting Documentation and Operational Considerations

